945 may jeopardize the participant or may require medical/surgical intervention to prevent one of
946 the outcomes listed above).

947 Unanticipated Adverse Device Effect (UADE): Any serious adverse effect on health or safety or
948 any life-threatening problem or death caused by, or associated with, a device, if that effect,
949 problem, or death was not previously identified in nature, severity, or degree of incidence in the
950 investigational plan or application (including a supplementary plan or application), or any other
951 unanticipated serious problem associated with a device that relates to the rights, safety, or
952 welfare of participants (21 CFR 812.3(s)).

953 Adverse Device Effect (ADE): Any untoward medical occurrence in a study participant which
954 the device may have caused or to which the device may have contributed (Note that an Adverse
955 Event Form is to be completed in addition to a Device Deficiency or Issue Form, unless excluded
956 from reporting as defined in section 6.2).

957 Device Complaints and Malfunctions: A device complication or complaint is something that
958 happens to a device or related to device performance, whereas an adverse event happens to a
959 participant. A device complaint may occur independently from an AE, or along with an AE.
960 An AE may occur without a device complaint or there may be an AE related to a device
961 complaint. A device malfunction is any failure of a device to meet its performance specifications
962 or otherwise perform as intended. Performance specifications include all claims made in the
963 labeling for the device. The intended performance of a device refers to the intended use for
964 which the device is labeled or marketed. (21 CFR 803.3). Note: for reporting purposes, sites
965 will not be asked to distinguish between device complaints and malfunctions.

966 **6.1.2 Reportable Adverse Events**

967 For this protocol, a reportable adverse event includes any untoward medical occurrence that
968 meets one of the following criteria:

- 969 1. An SAE
970 2. An ADE as defined in section 6.1.1, unless excluded from reporting in section 6.2
971 3. An AE as defined in section 6.1.1 occurring in association with a study procedure
972 4. An AE as defined in section 6.1.1 which leads to discontinuation of a study device for 2 or
973 more hours
974 5. Hypoglycemia meeting the definition of severe hypoglycemia as defined below

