975 6. Diabetic ketoacidosis (DKA) as defined below or in the absence of DKA, a hyperglycemia or
976 ketosis event meeting the criteria defined below

977 Hypoglycemia and hyperglycemia not meeting the criteria below will not be recorded as adverse
978 events unless associated with an Adverse Device Effect. Skin reactions from sensor placement
979 are only reportable if severe and/or required treatment.

980 Pregnancy occurring during the study will be reported as an AE (see section 6.3).

981 All reportable AEs—whether volunteered by the participant, discovered by study personnel
982 during questioning, or detected through physical examination, laboratory test, or other means—
983 will be reported on an AE form online. Each AE form is reviewed by the Medical Monitor to
984 assess safety and to verify the coding and the reporting that is required.

985 **6.1.2.1 Hypoglycemic Events**

986 Hypoglycemia not associated with an Adverse Device Effect is only reportable as an adverse
987 event when the following definition for severe hypoglycemia is met: the event required
988 assistance of another person due to altered consciousness, and required another person to actively
989 administer carbohydrate, glucagon, or other resuscitative actions. This means that the participant
990 was impaired cognitively to the point that he/she was unable to treat himself/herself, was unable
991 to verbalize his/ her needs, was incoherent, disoriented, and/or combative, or experienced seizure
992 or loss of consciousness. These episodes may be associated with sufficient neuroglycopenia to
993 induce seizure or loss of consciousness. If plasma glucose measurements are not available
994 during such an event, neurological recovery attributable to the restoration of plasma glucose to
995 normal is considered sufficient evidence that the event was induced by a low plasma glucose
996 concentration.

997 **6.1.2.2 Hyperglycemic/Ketotic Events**

998 Hyperglycemia not associated with an Adverse Device Effect is only reportable as an adverse
999 event when one of the following 4 criteria is met:

- 1000 • the event involved DKA, as defined by the Diabetes Control and Complications Trial
1001 (DCCT) and described below

- 1002 • evaluation or treatment was obtained at a health care provider facility for an acute event
1003 involving hyperglycemia or ketosis
- 1004 • blood ketone level ≥ 1.0 mmol/L and communication occurred with a health care provider
1005 at the time of the event

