6.4 Timing of Event Reporting

1094 SAEs possibly related to a study device or study participation and UADEs must be reported to
1095 the Coordinating Center within 24 hours of the site becoming aware of the event. This can occur
1096 via phone or email, or by completion of the online serious adverse event form and device issue
1097 form if applicable. If the form is not initially completed, it should be completed as soon as
1098 possible after there is sufficient information to evaluate the event. All other reportable ADEs
1099 and other reportable AEs should be submitted by completion on the online form within 7 days of
1100 the site becoming aware of the event.

1101 The Coordinating Center will notify all participating investigators of any adverse event that is
1102 serious, related, and unexpected. Notification will be made within 10 days after the Coordinating
1103 Center becomes aware of the event.

1104 Each principal investigator is responsible for reporting serious study-related adverse events and
1105 abiding by any other reporting requirements specific to his/her Institutional Review Board or
1106 Ethics Committee.

1107 Upon receipt of a UADE report, the Sponsor will investigate the UADE and if indicated, report
1108 the results of the investigation to the sites' IRBs, and the FDA within 10 working days of the
1109 Sponsor becoming aware of the UADE per 21CFR 812.46(b) (2). The Medical Monitor must

1110 determine if the UADE presents an unreasonable risk to participants. If so, the Medical Monitor
1111 must ensure that all investigations, or parts of investigations presenting that risk, are terminated
1112 as soon as possible but no later than 5 working days after the Medical Monitor makes this
1113 determination and no later than 15 working days after first receipt notice of the UADE.

1114 In the case of a device system component malfunction (e.g. pump, CGM, control algorithm),
1115 information will be forwarded to the responsible company by the site personnel, to be handled
1116 by its complaint management system.

1117 **6.5 Stopping Criteria**

1118 **6.5.1 Participant Discontinuation of Study Device**

1119 Rules for discontinuing study device use are described below.

- 1120 • The investigator believes it is unsafe for the participant to continue on the intervention. This
1121 could be due to the development of a new medical condition or worsening of an existing

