1122 condition; or participant behavior contrary to the indications for use of the device that
1123 imposes on the participant's safety
- 1124 • The participant requests that the treatment be stopped
- 1125 • Participant pregnancy
- 1126 • Two distinct episodes of DKA
- 1127 • Two distinct severe hypoglycemia events as defined in section 6.1.2.1

1128 Even if the study device system is discontinued, the participant will be encouraged to remain in
1129 the study through the final study visit.

1130 **6.5.2 Criteria for Suspending or Stopping Overall Study**

1131 In the case of an unanticipated system malfunction resulting in a severe hypoglycemia or severe
1132 hyperglycemia event (as defined in section 6.1.2), use of the study device system will be
1133 suspended while the problem is diagnosed.

1134 In addition, study activities could be similarly suspended if the manufacturer of any constituent
1135 study device requires stoppage of device use for safety reasons (e.g. product recall). The
1136 affected study activities may resume if the underlying problem can be corrected by a protocol or
1137 system modification that will not invalidate the results obtained prior to suspension.

1138 The study Medical Monitor will review all adverse events and adverse device events that are
1139 reported during the study and will review compiled safety data at periodic intervals (generally
1140 timed to the review of compiled safety data by the DSMB). The Medical Monitor may request
1141 suspension of study activities or stoppage of the study if deemed necessary based on the totality
1142 of safety data available.

1143 **6.6 Independent Safety Oversight**

1144 A Data and Safety Monitoring Board (DSMB) will review compiled safety data at periodic
1145 intervals (typically every 6 months). In addition, the DSMB will review all DKA and severe

1146 hypoglycemia irrespective of relatedness to study device use, and all serious events (including
1147 UADEs) related to study device use at the time of occurrence. The DSMB also will be informed
1148 of any ADEs not meeting criteria for a UADE if the Medical Monitor requests the DSMB
1149 review. The DSMB can request modifications to the study protocol or suspension or outright
1150 stoppage of the study if deemed necessary based on the totality of safety data available. Details
1151 regarding DSMB review will be documented in a separate DSMB document.

1152 **6.7 Risks**

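### Protocol 6.4 allows up to 7 days to report DKA or severe hypoglycemia judged non-serious or unrelated, so the DSMB review of every such event promised in 6.6 is not assured to be timely

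*Protocol*

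**What the plan says.** **Reporting clock (Protocol 6.4).** Two classes are expedited: "SAEs possibly related to a study device or study participation and UADEs must be reported to" "the Coordinating Center within 24 hours of the site becoming aware of the event. This can occur" by phone, by email or on the online forms. Everything else that is reportable has the longer limit: remaining adverse device effects (ADEs) "and other reportable AEs should be submitted by completion on the online form within 7 days of" site awareness.

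**What is reportable (Protocol 6.1.2).** Serious adverse events (SAEs) are criterion 1. Severe hypoglycemia and DKA have criteria of their own, with no condition on seriousness or relatedness: "Hypoglycemia meeting the definition of severe hypoglycemia as defined below" (criterion 5) and "Diabetic ketoacidosis (DKA) as defined below or in the absence of DKA, a hyperglycemia or" ketosis event meeting the stated thresholds (criterion 6).

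**DSMB review (Protocol 6.6).** Compiled safety data are reviewed at "intervals (typically every 6 months). In addition, the DSMB will review all DKA and severe" hypoglycemia, irrespective of relatedness. The same sentence adds all serious events (including "UADEs) related to study device use at the time of occurrence. The DSMB also will be informed" of certain other device effects at the Medical Monitor's request. Further detail is left to a separate DSMB document.

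**Suspension (Protocol 6.5.2).** "In the case of an unanticipated system malfunction resulting in a severe hypoglycemia or severe" hyperglycemia event, device use is suspended while the problem is diagnosed. This trigger carries no seriousness condition and no reporting deadline of its own.

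**SAP 2.12** sets no faster clock. It says that the DSMB reviews safety data at intervals, with no formal stopping rules beyond the protocol's criteria.

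**The concern.** The reporting clock in 6.4 depends on seriousness and relatedness. For DKA and severe hypoglycemia, the review in 6.6 depends on neither. The board can review an event only after the Coordinating Center hears of it, so an event on the 7-day clock may reach the board well after it happened.

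This matters because event-level review is the board's main safeguard between compiled looks, which are typically six months apart. The Protocol Summary makes safety the primary outcome of Objectives 2 and 3. Section 8.9 offers no formal stopping rules other than the criteria in 6.5. What is at stake is the speed of safety oversight. The estimates are not affected, because the same events are eventually recorded under either clock.

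**Working it through.** No statistical figure is involved, so the check sets the sections side by side.

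**Step 1. Must these events be serious?** No.
- Severe hypoglycemia (6.1.2.1) requires altered consciousness and active help from another person. It does not require admission.
- DKA (6.1.2.2) requires symptoms, ketones, acidosis and treatment in a health care facility. That need not be an inpatient stay.
- The SAE definition (6.1.1) names inpatient hospitalization. It also covers life-threatening events and those the investigator judges medically significant, so some of these events will be SAEs, but not automatically.

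**Step 2. Could the unanticipated adverse device effect (UADE) route close the gap?** Not for non-serious events. The UADE definition in 6.1.1 is built on serious effects or problems, life-threatening problems and death.

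**Step 3. Classify each DKA or severe hypoglycemia event.** Related here means possibly related to a device or to participation.

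| Site's judgment | Limit in 6.4 | Event-level review under 6.6 |
|---|---|---|
| Serious, related | 24 hours | Yes |
| Serious, unrelated | 7 days | Yes |
| Non-serious, related | 7 days | Yes |
| Non-serious, unrelated | 7 days | Yes |

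Three of the four combinations have the 7-day limit, yet 6.6 covers all four.

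**Step 4. Size of the permitted difference.** 7 days − 1 day = 6 days, counted from site awareness. Any delay before the site learns of the event adds equally to both clocks.

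**Step 5. Effect of a wrong causality call.** The Medical Monitor reviews each submitted adverse event form (6.1.2) and has the final say on causality (6.1.5). If a site wrongly calls a serious event unrelated, the longer clock can delay the review that would correct the call.

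**Step 6. The suspension trigger.** An event under 6.5.2 is caused by a malfunction, so it is device-related by construction.
- If it is serious and recognized as possibly related, it already has 24 hours.
- If it is judged non-serious, it is an ADE with 7 days. Examples are severe hypoglycemia treated at home, or ketones of at least 1.0 mmol/L with provider contact.
- If it is serious but first judged unrelated, it also has 7 days.

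Section 6.5.2 points to 6.1.2 for its definitions, but 6.1.2 defines DKA and reportable hyperglycemic/ketotic events and nothing called severe hyperglycemia. Which of those events count as triggers is therefore unclear.

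**The case against.** **The timing phrase in 6.6 may not bind.** It could attach only to the serious device-related events, or it could mean case by case as opposed to compiled, without setting a clock. A 24-hour limit from site awareness would not be literally at occurrence either. This has some force. But the sentence is introduced as an addition to periodic review. If the phrase did not reach DKA and severe hypoglycemia, they would be singled out with no timing of their own.

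**Many events will be serious.** An event with seizure or loss of consciousness may well be classed as medically significant or life-threatening and, if possibly related, reported in 24 hours. This stands, and it narrows the gap. It does not close it, because the call is the investigator's and unrelated events stay on 7 days.

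**The separate DSMB document may set a faster route.** It may, but it was not available for this review and 6.4 does not refer to it.

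**Stronger readings that the documents do not support.**
- A reader might infer that the DSMB cannot review these events promptly. Seven days is a ceiling, and a site may report sooner.
- A reader might infer that any suspension trigger can go unreported for a week. Step 6 shows that serious, recognized ones cannot.
- A reader might infer that the participant-level stop in 6.5.1 is delayed. The site already knows of its own participant's events, and nothing makes that stop wait for a form.
- A reader might multiply the 6 days by the enrollment ceiling to obtain an exposure. With no event rate in the documents, headcount times deadline does not measure risk.

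**Conclusion.** The point holds as a mismatch between 6.4 and 6.6. For DKA and severe hypoglycemia judged non-serious or unrelated, timely event-level DSMB review is not assured, and the permitted reporting delay is up to 6 days longer than for related serious events. A narrower gap of the same length affects 6.5.2, for malfunction-caused events judged non-serious or first misjudged as unrelated.

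The conclusion rests on three assumptions: the natural reading of 6.6, no faster route for sites in the unseen DSMB document, and at least some of these events being classed as non-serious or unrelated. The documents give no event rates, so the number affected cannot be estimated. No analysis is invalidated, but the wording should be corrected because the protocol promises a review that its own reporting rule does not secure.

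**What to change.** In Protocol 6.4, add to the 24-hour class, regardless of seriousness or relatedness:
- every severe hypoglycemia event as defined in 6.1.2.1;
- every DKA event as defined in 6.1.2.2;
- any reportable hypoglycemic or hyperglycemic/ketotic event under 6.1.2 with a suspected system malfunction.

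State that phone or email notice is enough, with the form to follow, as 6.4 already permits for the present 24-hour class. Leave all other events at 7 days. The third item refers to reportable events under 6.1.2, so sites can apply it without a definition of severe hyperglycemia.

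Separately, reconcile that term in 6.5.2 with 6.1.2. The sponsor should say which events it means; this review proposes no threshold. Check that the separate DSMB document agrees with the revised 6.4.

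The cost is a short amendment with the IRB review required by 10.2, a memo to sites, and a small number of earlier notifications. No new data are collected and no treatment rule or analysis changes. The SAP version history places the study in follow-up after the initial 3 months, so the change can help only for the remaining follow-up.

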**The International Diabetes Closed Loop Protocol 3
(DCLP3X) Trial: A Pivotal Study of t:slim X2 with
Control-IQ Technology**

[figure not shown]
Extension Study

Statistical Analysis Plan

Version 1.0

September 9, 2019

Based on Protocol Version 6.0

I have compared this SAP with the protocol version listed above and confirmed they are consistent.

Note: The table shells will be included in a separate document

1

Version History

2

Version	Author	Approvers	Effective Date	Study Stage	Protocol Version
1.0	[name]	[name]	9/9/2019	Follow-up post the initial 3months. Interim safety analyses for October 4, 2019 DSMB meeting in progress.	6.0

3

4

Version	Revision Description
1.0	Original Version

5

6

7

Approvals

Role	Digital Signature or Handwritten Signature/Date
Author and Statistician: [name], JCHR	
Senior Statistician: [name], JCHR	
Coordinating Center Director: [name], JCHR	
Study PI: [name] , University of Virginia	
Sponsor: [name], University of Virginia	

8

9 **1. Study Overview**

10 The following table gives an overview of the DCLP3X study.

11

12 **Table 1. Study Overview**

PARTICIPANT AREA	DESCRIPTION
Title	The International Diabetes Closed Loop (iDCL) Trial: Pivotal Trial of t:slim X2 with Control-IQ Technology - Extension Study
Précis	An extension study for participants who completed a prior 6-month randomized controlled trial (RCT) of a closed loop system (Control-IQ) vs. sensor-augmented pump (SAP).
Investigational Device	t:slim X2 with Control-IQ and Dexcom G6 system
Objectives	
The objectives of the study are
 
(1) Among individuals who used CLC in the original RCT, to compare continued use of CLC (t:slim X2 with Control-IQ Technology) for 3 months versus switching to a Predictive Low-Glucose Suspend (PLGS) system (t:slim X2 with Basal-IQ Technology) for 3 months.(2) Among individuals who used SAP in the original RCT, to obtain additional safety data by initiating use of the Control-IQ system for 3 months.(3) For all participants, use of the CLC system between the end of 3-month period and the point that the system becomes commercially available in order to gather additional safety data
Study Design	
Objective 1: RCT with 1:1 randomization to intervention with CLC vs. PLGS for 3 months.
 
Objective 2: Observational study of initiation and use of CLC for 3 months.
 
Objective 3: Observational study of initiation and use of CLC for 3 months following use of PLGS for 3 months; use of CLC by all participants between end of 3-month period and the point that the system becomes commercially available in order to gather additional safety data.

Number of Sites	Seven US clinical sites
Primary Endpoint	
Objective 1: The primary efficacy outcome for the RCT is time in target range 70-180 mg/dL measured by CGM in CLC group vs. PLGS group over 3 months. Safety outcomes also will be assessed
 
Objective 2: The primary outcome is safety outcomes. Efficacy also will be assessed as a pre-post within participant analysis
 
Objective 3: The primary outcome is safety outcomes. Efficacy also will be assessed as a pre-post within participant analysis

Population	
Key Inclusion Criteria
 
• Successfully completed the original 6-month RCT within the prior 14 days 
Key Exclusion Criteria
 
• Use of any non-insulin glucose-lowering agents except metformin
Sample Size	Sample size is based on the number in the original RCT who successfully complete six months and sign consent to participate in this study (up to approximately 168 total).
Treatment Groups	
Objective 1
 
• Group 1: t:slim X2 with Control-IQ Technology and Study CGM• Group 2: t:slim X2 with Basal-IQ Technology and Study CGM

PARTICIPANT AREA	DESCRIPTION
Participant Duration Protocol Overview/Synopsis	3 months Eligible participants in the original RCT who agree to be part of the Extension Study will sign the informed consent form. 
 • Participants assigned to the original RCT SAP group will initiate use of the CLC system for 3 months. • Participants assigned to the original RCT CLC group will be randomly assigned 1:1 to either continue CLC or switch to PLGS for 3 months. • After 3 months, all participants will be given the opportunity to use the CLC system until the point that the system becomes commercially available

13

14

15 The following table provides an overview of the schedule of study visits, phone contacts, and key
16 procedures.

17

18 **Table 2: Schedule of Visits and Procedures**

19

	0 Weeks	1w	2w	13w	26w, then every 13 weeks until end	Final Visit
Visit (V) or Phone (P)	V	P ¹	P ¹	V	V	V
Comment	Screen/Enroll and Rand/Assign					
Eligibility Assessment	X					
HbA1c (DCA Vantage or similar point of care device, or local lab)	X ²			X	X	X
HbA1c (Central lab)	X ²			X		
Pregnancy test (females of child-bearing potential)	X			X	X	
Device Data download(s)		X	X	X	X	X
Review diabetes management and AEs		X	X	X	X	X
Questionnaires	X ²			X	X ³	X
Follow-up Phone Call						P

20
21 ¹ Only performed for those participants who switched from SAP in the original 6-month RCT to CLC in the
22 Extension Study, or from CLC in the original RCT to PLGS in the Extension Study
23 ² Will use results obtained at Final Visit of preceding 6-month RCT

24 ³ 26-Week visit only

25

26

27

2. Objective 1

28 Among individuals who used CLC in the preceding 6-month RCT, to compare continued use of CLC
29 (t:slim X2 with Control-IQ Technology) for 3 months versus switching to a Predictive Low-Glucose
30 Suspend (PLGS) system (t:slim X2 with Basal-IQ Technology) for 3 months.31

- 32 Design and Primary Outcome: RCT with 1:1 randomization to intervention with CLC vs.
33 PLGS for 3 months. All analyses (treatment group comparisons) will be considered
34 exploratory/hypothesis-generating. Consequently, there will not be an attempt to adjust for
35 multiplicity. Time-in-range 70-180 mg/dL will be considered the primary exploratory
outcome.
- 36 Sample Size: The sample size will depend on how many subjects complete
37 the preceding 6-month RCT and consent to participate in the extension.
38 However, it is expected that about 100 subjects will be enrolled and
39 randomized for Objective 1.

40

